5.1 Study visit

5.1.1 Screening

Potential subjects will be identified by the research staff and medical staff who care for patients with PAH at Penn Medicine. After reviewing the potential subject's chart to see if she meets most of the inclusion/exclusion criteria, the subject will be approached by a research team member during a scheduled PH clinic visit. The study will be explained to the subject. After all questions are answered and if the subject agrees to participate, she will be scheduled for a screening visit.

The following procedures will be performed during the screening process:

- Review of inclusion/exclusion criteria
- Sign and date the informed consent and HIPAA release (must be done before any study procedures)
- Review medical history
- Review current medications
- Labs/Phlebotomy: complete blood count, hepatic function panel, platelet count, coagulation studies, and FSH (if needed)
- Provide instructions on recording of new concomitant medications and dose changes
- Instruct subjects to bring a list of routine medications to baseline visit, do not eat or drink (except water) 12 hours before baseline visit, and to avoid heavy exercise for 12 hours before the baseline visit

If the subject meets the inclusion/exclusion criteria for the study, the subject will be scheduled for a baseline study visit within 28 days at the study center. The research coordinator will call the subject and the PAH clinician 24 hours after the study visit if laboratories were obtained.

The screening visit can be combined with the baseline visit for participants who are known to be post-menopausal (i.e., (1) > 50 years old and have not menstruated during the preceding 12 months or (2) have undergone bilateral oophorectomy). Review of medical history, medications, and informed consent must be obtained prior to the combined visit.

5.1.2 Study Day – Visit 1 (Baseline), Day 0 (– 2 days)

The research coordinator will call the subject 1-2 days before the visit as a reminder to not eat or drink (except water) and to avoid heavy exercise for 12 hours before the study day assessment. Subjects will be instructed to bring a list of the current medications and to take all medications before the visit other than any oral PAH medication(s). The subject should bring her oral PAH medication(s) with her to be taken

after the blood draw. The subject will be reminded to wear appropriate clothing and shoes to complete a 6MWT.

Baseline information will be used to characterize the participants. Safety laboratories obtained at the screening visit will be used as baseline measurements. All baseline data will be collected prior to study drug administration. If a combined Screening Visit and Baseline Visit is performed, all labs (other than FSH for female subjects who are known to be post-menopausal per inclusion criteria) must be confirmed and all inclusion/exclusion criteria must be met prior to study drug administration.

The subject will arrive at the study site outpatient clinic. The following procedures will be performed:

- Vital signs
- Labs/Phlebotomy: estradiol level, NT-proBNP, hematopoietic progenitor cells (EPCs), and other research labs*
- Echocardiography
- Interim medical history
- Review current medications
- WHO functional class assessment (must be done by a study physician or research nurse)
- Physical exam
- Six minute walk testing (6MWT) with Borg scores
- Assess any adverse events (AEs) or serious adverse events (SAEs) that have occurred since last visit
- Review of inclusion/exclusion criteria
- Administration of study drug, fulvestrant, by the study physician or research nurse
- Reinforce instructions on recording of new medications and dose changes

*Screening labs should be drawn if performing a combination baseline/screening visit. All screening laboratory tests must be received and all inclusion/exclusion criteria confirmed by the PI before the subject can receive study drug.

There is no particular order in which these procedures must be done EXCEPT for the administration of the study drug, which should be performed last and only if the subject is eligible per inclusion/exclusion criteria.

Blood samples for research study assays will be kept a room temperature and shipped to be processed as well as processed on site and banked in a freezer at -70° C.

Echocardiography will be performed. The PI or research nurse will take a history and perform a physical examination and the subject will complete the 6MWT.

The study medication will be administered last by the research nurse or physician. It will be administered according to the manufacturer's instructions. 500 mg will be given as two intramuscular injections to eligible subjects who do not have Child-Pugh Class B liver disease and 250 mg for eligible subjects who have Child-Pugh Class B liver disease. Each syringe holds 250 mg of fulvestrant.

After the completion of the baseline visit, the research coordinator will thank the subject for their attendance and reinforce compliance with the visit schedule. The subject's primary PAH physician and medical doctor will be alerted to the subject's participation in the clinical trial. The next clinic visit (Visit 2) will be scheduled for Week 2 ± 3 days.

5.1.3 Visit 2, Week 2 (Two weeks ± 3 days)

The research coordinator will call the subject 1-2 days before the visit as a reminder. Subjects will be instructed to bring a list of the current medications and to take all medications before the visit.

The subject will arrive at the study site outpatient clinic. The following procedures will be performed:

- Interim medical history
- Assess any AEs/SAEs
- Vital signs
- Review current medications
- Study drug administration by study physician or research nurse
- Reinforce instructions on recording of new medications

The study medication will be administered last by the research nurse or a study physician. It will be administered according to the manufacturer's instructions. 500 mg will be given as two intramuscular injections to eligible subjects who do not have Child-Pugh Class B liver disease and 250 mg for eligible subjects who have Child-Pugh Class B liver disease. Each syringe holds 250 mg of fulvestrant.

The research coordinator will thank the subject for their attendance, schedule the next visit and reinforce compliance with the study visit timeline.

5.1.4 Visit 3, Week 4 (Four weeks ± 3 days)

The research coordinator will call the subject 1-2 days before the visit as a reminder. Subjects will be instructed to bring a list of the current medications and to take all medications before the visit.

The subject will arrive at the study site outpatient clinic. The following procedures will be performed:

- Interim medical history
- Assess any AEs/SAEs

- Vital signs
- Review current medications
- WHO functional class assessment (must be done by study physician or research nurse)
- Physical exam
- Study drug administration by the study physician or research nurse
- Reinforce instructions on recording of new medications

The study medication will be administered last by the research nurse or physician. It will be administered according to the manufacturer's instructions. 500 mg will be given as two intramuscular injections to eligible subjects who do not have Child-Pugh Class B liver disease and 250 mg for eligible subjects who have Child-Pugh Class B liver disease. Each syringe holds 250 mg of fulvestrant.

The research coordinator will thank the subject for their attendance, schedule the next study visit and reinforce compliance with the study visit timeline.

5.1.5 Visit 4, Week 8 (Eight weeks \pm 3 days)

The research coordinator will call the subject 1-2 days before the visit as a reminder. Subjects will be instructed to bring a list of the current medications and to take all medications before the visit.

The subject will arrive at the study site outpatient clinic. The following procedures will be performed:

- Interim medical history
- Assess any adverse events/serious adverse events
- Vital signs
- Review current medications
- Study drug administration by study physician or research nurse
- Reinforce instructions on recording of new medications

The study medication will be administered last by the research nurse or physician. It will be administered according to the manufacturer's instructions. 500 mg will be given as two intramuscular injections to eligible subjects who do not have Child-Pugh Class B liver disease and 250 mg for eligible subjects who have Child-Pugh Class B liver disease. Each syringe holds 250 mg of fulvestrant.

The research coordinator will thank the subject for their attendance, schedule the final study visit and reinforce compliance with the study visit timeline.

5.1.6 Visit 5 (Nine weeks -3 or + 7 days)

The research coordinator will call the subject 1-2 days before the visit as a reminder. The coordinator will instruct the subject to not eat or drink (except water) and to avoid heavy exercise for 12 hours before the study day assessment. Subjects will be instructed

to bring a list of the current medications and to take all medications before the visit other than any oral PAH medication(s). The subject should bring their oral PAH medication(s) with them to be taken after the blood draw. The subject will be reminded to wear appropriate clothing and shoes to complete a 6MWT.

The subject will arrive at the study site outpatient clinic. The following procedures will be performed:

- Labs/Phlebotomy: research labs
- Echocardiogram
- Interim medical history
- Assess any adverse events/serious adverse events
- Vital signs
- Review current medications
- WHO functional class assessment
- Physical exam
- 6MWT with Borg scores

There is no particular order in which these procedures must be done, but it is recommended that the fasting blood draw be performed first.

Blood samples for study assays will be processed and banked. After obtaining the blood samples, the subject will be instructed to take their regular medications.

Echocardiography will be performed. The investigator or research nurse will take a history and perform a physical examination. The subject will complete the 6MWT.

The research coordinator will thank the subject for their participation in the clinic visits of the clinical trial. A follow-up phone call will be scheduled.

5.1.7 Follow-up Phone Call (Twelve weeks ± 3 days)

The research coordinator will call the subject. The following will be reviewed:

- Any changes in concomitant medication
- Review all adverse events/serious adverse events
- Interim medical history

If there is a significant increase in symptoms or worsened clinical status the subject will be asked to come to the study center for evaluation.

5.1.8 End of Study Visit for Early Withdrawal Subjects

If a subject withdraws or is withdrawn from the study, they will come to clinic for an End of Study Visit. The procedures done at Visit 5, Week 9 will be performed (see Section 5.1.6.) A follow-up phone call will be done at week 12 if the subject agrees.

5.2 Study schedule of procedures

The table below summarizes the study procedures.

Table 1. Study Procedures

	Screening*	Baseline	Week 2	Week 4	Week 8	Week 9	Week 12 Follow-up Phone Call
Visit #		1	2	3	4	5	
Day#	-28 - 0	-2 - 0	14 ± 3	28 ± 3	56 ± 3	- 3- (63) + 7	84 ± 3
Informed consent	X						
General Testing							
Physical Exam		X		X		X	
Medical history	X	X ^a					
Vital signs	X	X	X	X	X	X	
WHO FC Assessment		X		X		X	
Laboratory Test							
Complete blood count	X	X ^a					
Hepatic function panel	X	X ^a					
Coagulation studies (PT/INR)	X	X ^a					
FSH	X	X ^a					
Research labs		X				X	
Study procedures							
Study drug administration		X	X	X	X		
Echocardiogram	X	X ^a				X	
Six minute walk test		X				X	
Concomitant Medications	X	X	X	X	X	X	X
Assess Adverse Events/Serious Adverse Events		X	X	X	X	X	X

X^a: Only to be performed if not done at screening visit. These assessments should be reviewed by the PI prior to first administration of study drug to ensure that the subject meets inclusions/exclusion criteria.

*Screening Visit procedures may be done at the Baseline Visit for female participants who are known to be post-menopausal: (1) > 50 years old and have not menstruated during the preceding 12 months or (2) have undergone bilateral oophorectomy. Review of medical history, medications, and informed consent must be obtained prior to the combined visit.

5.3 Subjects' retention and drug compliance

We will enforce subject retention in several ways. We will record extensive contact information for each subject at their enrollment in the trial. This will include home, work, and cellular telephone numbers. The research coordinator will call before each study visit to remind the subject to attend. The research coordinator and physician will explain the importance of compliance with the study protocol at each subject contact. If a subject fails to comply with a study visit, the coordinator will contact her by telephone. If this fails, the coordinator will send two letters by UPS, one week apart, to request follow-up.

If a subject wishes to drop-out from the treatment phase of the study or has a serious adverse event (whether related to study drugs or not), we will continue to follow-up with the subject for study assessments to assist with safety monitoring and to avoid the problems introduced by missing data.

5.4 Subject reimbursement

Subjects will be reimbursed for reasonable travel expenses and the inconvenience of the study procedures necessary for participation. We acknowledge that participation in this study is very burdensome due to many factors such as the route of administration of the study drug, the time needed to complete procedures associated with the study, and the frequent trips to the clinic to perform study procedures. The subject will be reimbursed \$100 for completing the screening visit. Each subsequent visit completed (visits 1-5) will be reimbursed \$250 for a total reimbursement of \$1350.

The study drug will be provided free of charge.

Chapter 6. Outcome Measures

6.1 Assessments of efficacy

- E2 levels and HPCs
- RV systolic pressure, tricuspid annular plane systolic excursion (TAPSE), and RV stroke volume index
- Six-minute walk distance
- Plasma NT-proBNP level
- Safety and side effects associated with short-term fulvestrant administration in subjects with PAH

6.1.1 Plasma Estradiol (E2) Levels

Plasma E2 levels will be measured using a double antibody radioimmunoassay.

6.1.2. Hematopoietic Progenitor Cells (HPCs)

Plasma HPC levels will be measured using flow cytometry.

6.1.3 Echocardiographic Measures

The ultimate determinant of outcome in subjects with PAH is RV function which will be measured by transthoracic echocardiography. Thus, we have focused on TAPSE, which reflects RV shortening and is a strong predictor of survival in PAH. We will also assess RV systolic pressure, stroke volume index, RV fractional area change and other parameters.

6.1.4 Six minute walk distance

Walking is the most basic form of exercise and is integral to daily activities. The 6MWT is a standardized, timed submaximal test of unencouraged, self-determined distance walked which is reliable and valid. We will use standardized test methods as well as scripted and timed statements that have been established in prior studies of PAH that have been recommended by the American Thoracic Society in 2002. The 6WMT is also non-invasive and safe.

The subject will be instructed to wear comfortable clothing and shoes. The test will be performed at approximately the same time of day at each visit. The Borg score for dyspnea and oxygen saturation will be recorded at the beginning and conclusion of each test.

6.1.5 Plasma NT-pro BNP

Plasma NT-proBNP reflects right ventricular function in PAH and is a very strong predictor of outcome in PAH.

6.1.6 WHO functional class

The WHO functional classification for PAH has been modified from the well-known New York Heart Association functional classification. This functional classification is based on

symptoms, with Class I being defined by no symptoms with physical activity, Class II as having mild limitation in physical activity and are comfortable at rest, Class III as having markedly limited physical activity and are comfortable at rest, and Class IV as being unable to perform any physical activity without symptoms. The WHO functional class will be assessed at baseline, Week 4 and Week 9.

Chapter 7. Statistical Considerations

7.1 Study design

To address the aims of this study, we will conduct an open-label, single-arm trial. Blood sampling, echocardiography and 6MWT will be performed at baseline and nine weeks.

7.2 Disposition of subjects and baseline summaries

Summaries of all subjects screened and recruited, and the number who complete visits at baseline, week two, week four, week eight, and week nine will be provided, according to the CONSORT guidelines.

7.3 Statistical procedures

7.3.1 Data analysis

Prior to the formal analysis, the distributions of the key variables to be used in the analyses will be examined using summary statistics and graphical tools.

Outcomes of interest will be evaluated with a per-protocol analysis. Subjects who are not compliant or stop the treatment portion of the study will be replaced (although their data will also be considered in secondary analyses). Outcomes include estradiol levels, TAPSE and other echocardiographic measures, 6MWD, plasma NT-proBNP level, and other variables as well as safety and side effects.

These measures will be assessed both at baseline and nine weeks. Summary statistics will be produced with both the repeated measures as well as the calculated differences from the baseline. We will summarize demographics and other predictors of clinical status. Continuous variables will be summarized by the mean, median, standard deviation, and range, as appropriate. We will use contingency tables for discrete and dichotomous variables.

Hypothesis testing will use two-sided $\alpha= 0.05$. All statistical analyses will be performed using SAS and R.

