7.3.2 Univariate analysis

Univariate analyses will be performed for all variables of interest. These will be carried out by comparing the changes from baseline using signed rank tests for continuous variables and McNemar's test for categorical variables.

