7.3.3 Missing data and dropouts

Patients who drop out from treatment or assessment plan will be replaced.

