9.5 Other events

We will not discontinue study drug for clinical events not thought to be serious drug-related AEs. For example, a hospitalization for clinical worsening will not result in cessation of trial participation. Such events could result in missing data for primary and secondary endpoints, comprising the integrity of the analysis. As the trial does not prohibit any therapies which is the standard of care in PAH, there is no ethical or safety reason to stop trial participation under such circumstances. Even if subjects are withdrawn from the study drug outcome assessments will continue. Subjects who are not compliant or stop the treatment portion of the study will be replaced.

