9.6.5 Subject withdrawal

A subject has the right to withdraw from the study entirely at any time for any reason without prejudice to future medical care by the investigator or other physician. The investigator also has the right to withdraw subjects from the study in the event of concurrent illness, AEs, or other reasons deemed to be in the subject's best interest.

A subject should be withdrawn from the study if there is:

- Withdrawal of consent
- Termination of the study by the funding agency

In order to preserve the integrity of the study, even if the subject is withdrawn from the treatment portion of the protocol (either due to subject, physician, or investigator decision), we will continue with the scheduled follow-up assessments both for the safety of the subject and for completeness of data collection. This will be explained to potential subjects at the time of informed consent. The importance of compliance with study visits will be reinforced throughout the trial. If the both treatment is permanently withdrawn, the subject will return to the center for safety assessment (history, physical examination, and clinical laboratories, if necessary). In the event of clinical worsening, subjects will be continued on their assigned study medication. If a subject develops an indication for fulvestrant therapy (such as breast cancer), the subject will be withdrawn from receiving study drug in this clinical trial but will continue to be assessed per protocol.

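### Per-protocol membership is undefined and not fixed before week-9 results, values held on replaced subjects are left out of the leading estimate, and the 0.05 rule cannot be met with five subjects

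*Combined protocol and SAP*

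**What the plan says.** **Analysis set.** Section 7.3.1 states: "Outcomes of interest will be evaluated with a per-protocol analysis". Its next sentence gives the rule for replacing subjects: "not compliant or stop the treatment portion of the study will be replaced (although their data will also be considered in secondary analyses". Section 9.5 repeats this replacement rule. Section 7.3.3, the whole of the plan for missing data, is one sentence: "Patients who drop out from treatment or assessment plan will be replaced". It does not mention non-compliance, and it adds leaving the assessment plan as a ground for replacement. The grounds can be read as cumulative. No section defines compliance or says when membership of the per-protocol set is decided.

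**Data collected after stopping.** Section 9.5: "Even if subjects are withdrawn from the study drug outcome assessments will continue". Section 9.6.5: "we will continue with the scheduled follow-up assessments both for the safety of the subject and for completeness of data collection". Section 5.3 gives the avoidance of missing data as one reason for this follow-up. Section 5.1.8 gives subjects withdrawn from the study the Visit 5 procedures at an End of Study Visit, without fixing its timing.

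**Testing.** Section 7.3.1: "These measures will be assessed both at baseline and nine weeks". It then says "Hypothesis testing will use two-sided" alpha of 0.05. Section 7.3.2 specifies "comparing the changes from baseline using signed rank tests for continuous variables". The Protocol Summary sets enrolment at 5. Section 7.4 says that no power calculation was done and that the study is for hypothesis generation and feasibility.

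**The concern.** With a single arm, the change from baseline in the analysed subjects is the whole efficacy result, so who is counted matters more than usual. Three things follow from the text.

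1. Membership turns on an undefined word. In an open-label study the people deciding who was compliant may already know that subject's week-9 walk distance or echocardiogram. Nothing in the plan prevents this.
2. The plan keeps measuring subjects who stop, partly to avoid missing data, and then leaves their week-9 values out of the result that leads. If those who leave differ in outcome from those who stay, the leading estimate describes subjects who tolerate the drug.
3. The plan sets a significance rule that the per-protocol set of five cannot meet. A secondary set enlarged by a replaced subject can meet it.

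**Working it through.** **Inputs from the documents:** 5 subjects (Protocol Summary); two-sided 0.05 (7.3.1); signed rank test on change from baseline (7.3.2). The plan states no power figure, stopping rate or SD, so there is no figure of its own to reproduce.

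**Assumptions:** replacement continues until 5 compliant subjects have week-9 values; stopping probability p is 10% or 20%; correlation rho between the tendency to stop and the outcome is 0, 0.3 or 0.5.

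**A. What the test can show.** With n non-zero, untied changes, the most extreme result is all n in one direction. The smallest exact two-sided p is 2/2^n.
- n=5: 2/32 = 0.0625. It cannot reach 0.05.
- n=6: 2/64 = 0.03125, if all six move the same way.
- n=7: 2/128 = 0.0156.

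The chance of p ≤ 0.05 when there is no true change is 0 at n=5, 3.1% at n=6 and 4.7% at n=7 (by enumeration, rank sums up to 2 qualify at n=7).

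The plan does not say that the exact test is meant. With all five changes in one direction, the rank sum is 15, its null mean 7.5 and its null SD √(5×6×11/24) = 3.708. A normal approximation without continuity correction gives z = 7.5/3.708 = 2.02 and p = 0.043. With the correction, z = 7/3.708 = 1.89 and p = 0.059. So at n=5 crossing 0.05 would depend on the approximation used.

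**B. How often the larger set would arise.** The chance that at least one subject is replaced before five complete is 1−(1−p)^5: 41% at p=10% and 67% at p=20%. This is also the chance of n ≥ 6 if every stopper gives a week-9 value. If half do, it is 1−((1−p)/(1−p/2))^5: 24% and 45%. If none do, it is 0.

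**C. Possible shift in the per-protocol mean.** Shift = rho × φ(z_p)/(1−p), in SD of the change.

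| p | rho 0 | rho 0.3 | rho 0.5 |
|---|---|---|---|
| 10% | 0 | 0.0585 | 0.0975 |
| 20% | 0 | 0.105 | 0.175 |

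The standard error at n=5 is 1/√5 = 0.447 SD, so the non-zero shifts are 13% to 39% of one standard error. With variance held fixed, root-mean-square error rises by a factor of √(1+0.131²) to √(1+0.391²), about 1% to 7%.

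**D. What adding the replaced subjects does.** In simulation (dosing until 5 completers, 100,000 runs per case, rho 0.3–0.5), the remaining shift in the all-dosed mean is 0.01–0.02 SD if every stopper gives a week-9 value, 0.03–0.09 SD if half do, and essentially unchanged if none do.

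Those figures give subjects off drug no loss of effect. Under the same model stoppers average 8% (p=10%) to 17% (p=20%) of the all-dosed set when all give values. If stopping costs an assumed 0.5 SD of effect, dilution is 0.04–0.09 SD. The selection shift removed is about 0.05–0.15 SD (0.0585−0.010 to 0.175−0.022). The two are of similar order.

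**E. Difference between the two reported means.** With d replaced subjects who all give values, per-protocol mean minus all-dosed mean = d/(5+d) × gap, where gap is the completer-minus-replaced difference. For an assumed gap of 0.5–1.5 SD this is 0.08–0.25 SD at d=1 and 0.14–0.43 SD at d=2. Only the last extreme comes close to one standard error.

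**The case against.** Per-protocol is a legitimate question for a proof-of-concept study, and the plan chooses it openly. It also says that replaced subjects' data will be used, most naturally by adding them to the per-protocol subjects. Time points and tests are stated. Sections 9.5 and 9.6.5 keep clinically worsening subjects on drug, which closes the most obvious route to selection. The possible shift rests on assumed inputs and is modest beside sampling error. An all-dosed estimate carries dilution of its own. The signed-rank floor comes from n=5, whoever is replaced.

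Most of this stands, and it rules out several stronger readings that a reader might infer:
- *That the all-dosed result must come first.* Sections C and D of the working do not show that it is the less biased estimate of the on-drug effect, so the order is a matter of choice.
- *That the per-protocol result is materially inflated.* The documents give neither the direction nor the size of any bias.
- *That attrition is hidden.* Section 7.2 reports everyone screened and recruited, with completion by visit; 7.6 documents violations.
- *That safety is analysed per-protocol.* Safety appears in the list in 7.3.1, but 7.7 includes all subjects and governs.
- *That false positives exceed 5%.* With the exact test, no set of 5, 6 or 7 exceeds 4.7%.

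The objection leaves three gaps unanswered. Selection is limited but not excluded, because 9.6.5 lets subjects leave by choice and lets the investigator withdraw them for adverse events or concurrent illness. Nothing defines compliance or fixes membership in advance. And 7.3.1 sets a significance rule that the exact test cannot satisfy in its own leading set.

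**Conclusion.** The point holds in a limited form and is worth fixing before analysis.

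Two parts are plain from the text: compliance, which decides both replacement and membership, is undefined with no requirement to settle it before week-9 results are known; and the leading estimate omits week-9 values collected on replaced subjects. The consequence for bias is uncertain in direction and size. It is nil if stopping is unrelated to outcome, 0.06–0.17 SD under the assumptions above, and probably small beside a standard error of 0.45 SD.

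The testing part needs no assumption about stopping rates, only a per-protocol set of five and the exact test. Rejection at 0.05 is impossible at n=5 and possible at n=6, so nominal significance would depend on someone being replaced, having a week-9 value and changing in the same direction as the other five.

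**What to change.** In 7.3.1, with matching wording in 7.3.3 and the Protocol Summary:

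1. Keep the per-protocol result. Define non-compliance (the definition is for the investigators to choose) and record each subject's membership in writing before her week-9 results are seen.
2. Beside it, report the change from baseline in all subjects who received at least one injection and have baseline and week-9 values, including replaced subjects. Show this with and without any End of Study values taken before week 9.
3. Remove the significance rule at 0.05. Present both results as descriptive estimates. If p-values are shown, name the version of the test and give n and the smallest attainable p.

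The order of the two results and the mention of safety in 7.3.1 can stay as they are.

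The cost is wording only: no new visits or data. The all-dosed estimate will be diluted by subjects off drug, and some added values may reflect shorter exposure. Subjects with no post-baseline value, for example after withdrawal of consent, remain excluded, so the gain is partial. If no replaced subject returns, the all-dosed result adds nothing to the per-protocol one.
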